## 9.3 Local Tolerability Assessments

Local tolerability assessments are performed for both axillae individually at visits 4, 5, 6, 7, 8, 9, 12 (EOT), and 13 (follow-up). Visit 4 data are the baseline. Should Visit 4 data be missing, baseline will be derived as the last value prior to first dose and as such unscheduled visits may be included. Subjects rate the severity of any symptoms of burning, stinging, or itching at the application-site on a scale of 0 = absent, 1 = minimal, 2 = mild, 3 = moderate, and 4 = severe. Investigators assess the drug application site for the existence of significant local symptoms of scaling and erythema on a scale of 0 = absent, 1 = minimal, 2 = mild, 3 = moderate, and 4 = severe. For any symptoms, subject severity is the worst severity of the two axillae.

Subject and Investigator assessments will be included in tables and listings. Tables will be presented by treatment arm. An overall summary table will be presented with subject incidences tabulated according to the worst severity experienced while on study. At each visit, local tolerability assessments will also be descriptively summarized by severity. Additionally, at each post-baseline visit, local tolerability will be summarized as cumulative shift tables vs. baseline. Subject counts for each symptom will be cross-tabulated with baseline severity according to the maximum post-baseline severity reported for either axilla up to the current visit. Local tolerability assessment results will also be plotted by severity, displaying counts for any symptom, burning, stinging, itching, scaling, and erythema. A symptom is counted if the severity scale is rated >0.

## 9.4 Clinical Laboratory Evaluation

Safety laboratory parameters (hematology, chemistry, urinalysis) will be collected at the Screening Visit and EOT Visit. Urine pregnancy results will be collected at visits 1, 4, 8,

Version: 2.0 Page 41 of 74

and 12 (EOT). Laboratory parameters will be presented in Systeme International (SI) units and descriptively summarized for values at each visit and for changes from baseline at each subsequent visit. Unscheduled visits and early termination visits will be included.

Laboratory parameters to be summarized and listed include hematology, clinical chemistry, and routine urinalysis. Urine pregnancy test results will be listed only.

# 9.5 Vital Signs, Physical Findings, and Other Observations Related to Safety

#### 9.5.1 Vital Signs

Vital signs measurements will be collected at Visits 4, 5, 6, 7, 8, 9, 12 (EOT), and 13 (follow-up). Visit 4 data are the Baseline. Should Visit 4 data be missing, baseline will be derived as the last value prior to first dose (e.g. Screening), and, as such, unscheduled visits may be included. Vital sign measurements will include systolic and diastolic blood pressure, pulse rate, respiratory rate, and temperature. Vital sign parameters will be descriptively summarized for values at each visit and for changes from baseline at each subsequent visit. Vital signs will also be listed.

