#### Risk to Subjects

As an anticholinergic drug, administration of sofpironium bromide gel could be associated with signs or symptoms typical of anticholinergic effect such as dry mouth, blurred vision, dizziness, constipation, urinary retention, or tachycardia. The previous sofpironium bromide exposure to humans has demonstrated a low incidence of these effects, which are generally mild in severity. All such effects have been observed, and as expected, to be transient.

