#### 7.3 Unscheduled Visits

If a subject is seen for an unscheduled visit, an assessment and record of AEs should be completed, as appropriate. Additional evaluations should be performed as necessary, and the appropriate CRF pages should be completed.

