#### **8.1.4** Adverse Events

Adverse events (AEs; see Section 9.2) will be collected for all untoward medical occurrences in a subject entered into this clinical study (e.g., signed consent), whether or not a pharmaceutical product has been administered. Any event, including local tolerability assessments (see Section 8.1.5), that requires specific treatment, results in interruption of treatment, or results in discontinuation of the subject from the study will also be reported as an AE.

Care will be taken not to introduce bias when detecting AEs and/or SAEs. Open-ended and non-leading verbal questioning of the subject is the preferred method to inquire about AE occurrence.

Appropriate questions include:

- "How are you feeling?"
- "Have you had any (other) medical problems since your last visit/contact?"
- "Have you taken any new medicines, other than those provided in this study, since your last visit/contact?"

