## 9.6 Other Safety Measures

Safety will also be assessed by physical examinations, laboratory tests, and measurement of vital signs assessed as indicated throughout the study schedule. Clinically significant changes in these parameters may be captured as adverse events.

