#### 9. SAFETY EVALUATION

## 9.1 Overview of Safety Analysis Methods

Safety analyses will be carried out for the Safety Population. Subjects who do not complete the study, for whatever reason, will have all available data up until the time of termination included in the analyses. Allowable windows for each study visit are laid out in the Schedule of Events in Section 18.1. Assessments that occur outside of the allowable window for each study visit will be flagged as protocol deviations, but will be used in all safety analyses. In general, all data will be associated with the nominal study visit for which it was collected. Repeat assessments and unscheduled visits will be included in study listings, but will not be used in place of nominal timepoint data. It is not expected that there will be multiple measurements that occur within the same assessment time window. Should that occur, the closest measurement will be used in the analysis; an earlier measure will be used in case of a tie. No formal hypothesis testing will be performed.

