	up) by System Organ Class, Preferred Term, and	
14.3.1.8.6	Maximum Severity	Safety
	Number and Percentage of Subjects with Treatment-	
	Emergent Adverse Events Leading to Study	
	Discontinuation Cumulative to Visit 13 (Day 57,	
142107	Follow-up) by System Organ Class, Preferred Term,	Cofoty
14.3.1.8.7	and Maximum Severity	Safety
	Number and Percentage of Subjects with Treatment-	
14.3.1.8.8	Emergent Adverse Events of Special Interest	Safety

Version: 2.0 Page 63 of 74

Number	Title	Population
	Cumulative to Visit 13 (Day 57, Follow-up) by System Organ Class, Preferred Term, and Maximum Severity	
14.3.1.8.9	Number and Percentage of Subjects with Anticholinergic Treatment-Emergent Adverse Events Cumulative to Visit 13 (Day 57, Follow-up) by System Organ Class, Preferred Term, and Maximum Severity Number and Percentage of Subjects with Local Site Reaction Treatment-Emergent Adverse Events Cumulative to Visit 14 (Day 57, Follow-up) by System Organ Class, Preferred Term, and Maximum Severity	Safety
14.3.4.1	Mean and Mean Change from Baseline in Serum Biochemistry Values by Visit	Safety
14.3.4.2	Mean and Mean Change from Baseline in Hematology Values by Visit	Safety
14.3.4.3	Mean and Mean Change from Baseline in Continuous Urinalysis Values by Visit	Safety
14.3.4.4	Categorical Urinalysis Values by Visit	Safety
14.3.5	Study Drug Administration Exposure and Compliance	Safety
14.3.6.1	Worst Post-baseline Severity for Local Tolerability Assessments by Treatment Group	Safety
14.3.6.2	Worst Severity for Local Tolerability Assessments by Treatment Group and Visit	Safety
14.3.6.3	Shift in Worst Severity for Local Tolerability Assessments from Baseline to Each Visit	Safety
14.3.6.4	Mean and Mean Change from Baseline in Vital Signs Values by Visit	Safety
14.3.6.5	Summary of Concomitant Medications by Drug Class and Generic Drug Name	Safety

Version: 2.0 Page 64 of 74

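### A high pulse that is measured but not reported as an adverse event is never counted by arm, because vital signs get only summary statistics by visit

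*SAP*

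**What the plan says.** Protocol Section 1, Risk to Subjects, lists the effects expected of an anticholinergic: "dry mouth, blurred vision, dizziness, constipation, urinary retention, or tachycardia". Pulse is counted over 60 seconds (Protocol 8.1.2) at Visits 4 to 9, 12 and 13. That gives one baseline, six on-treatment readings and one follow-up reading.

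For analysis, SAP 9.5.1 states: "Vital sign parameters will be descriptively summarized for values at each visit and for changes from baseline at each subsequent visit". A listing is added. SAP Section 15 has one vital-sign table, 14.3.6.4, titled "Mean and Mean Change from Baseline in Vital Signs Values by Visit". Section 16 has no vital-sign figure, and Section 17 has one vital-sign listing, 16.2.9.2. SAP 3.1 defines a continuous summary as mean, SD, minimum, maximum, median and n. Protocol 10.4 plans the same kind of summary and no more. Neither document sets a pulse limit, a shift table or a count of subjects.

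The route from a vital sign to an adverse event is Protocol 9.6: "Clinically significant changes in these parameters may be captured as adverse events". Protocol 8.1.4 is broader: adverse events "will be collected for all untoward medical occurrences in a subject entered into this clinical study". At an unscheduled visit, Protocol 7.3 says "an assessment and record of AEs should be completed, as appropriate".

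On data handling, SAP 9.1 says that subjects who stop early "will have all available data up until the time of termination included in the analyses". It also says: "Repeat assessments and unscheduled visits will be included in study listings, but will not be used in place of nominal timepoint data".

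**The concern.** A high pulse can reach a count by arm in only one way: the investigator records it as an adverse event, and it then enters the TEAE tables. That step is optional and has no numeric criterion. Adverse events are preferably elicited by open-ended questions, which may not bring out a fast pulse without symptoms. Tachycardia is also not among the TEAEs of special interest named in SAP 9.2.

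For a reading that is not recorded, the report offers a by-visit maximum and a listing. A reader who wants to know how many subjects on each arm had a high pulse would have to count by hand. Safety comes first among the primary objectives in SAP 2.1, and the pulse data needed for the count are already being collected.

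**Working it through.** **Text check.** The documents state no vital-sign figure, so there is nothing to reproduce. SAP 9.5.1, Table 14.3.6.4, Listing 16.2.9.2 and Protocol 10.4 agree with one another, and none of them gives a number of subjects.

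**Inputs.** From the documents: 175 per arm (Protocol Section 2) and six on-treatment readings. Assumed: normally distributed pulse with mean 74 bpm, between-subject SD 8 and within-subject SD 7, later varied over 70 to 80, 8 to 11 and 5 to 9. The limit of 100 bpm is applied to all 175 subjects here.

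**Can the mean show a small cluster?** Shift in the arm mean = share affected × rise. For 2% to 5% affected by 20 to 40 bpm, this is 0.02 × 20 = 0.4 to 0.05 × 40 = 2.0 bpm. The SE of the difference between arms is SD × √(2/175). With an assumed SD of 10 to 12 bpm, that is 1.07 to 1.28 bpm. The mean could miss such a cluster.

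**Can the maximum show a count?** Simulation with 4,000 trials per scenario. Affected subjects have the full rise at Visit 5, half at Visit 6 and none later.

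| Scenario, Visit 5 | Average maximum rise (bpm) | Subjects with pulse >100 and rise ≥20 |
|---|---|---|
| No effect | 26.8 | 0.3 |
| One subject at +50 | 50.0 | 1.3 |
| Five subjects at +40 | 51.5 | 4.7 |

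The maximum reacts to a large rise but does not separate one subject from five.

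**What would chance alone produce?** At a single visit, a change has SD 7 × √2 = 9.90, so P(rise ≥20) = P(Z ≥ 2.02) ≈ 0.022, or 175 × 0.022 ≈ 3.8 subjects. A single reading has SD √(8² + 7²) = 10.6, so P(>100) = P(Z > 26/10.6) ≈ 0.007, or about 1.3 subjects. Over any of the six visits, by simulation, per arm:

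| Mean / between SD / within SD | >100 | Rise ≥20 | Both |
|---|---|---|---|
| 70 / 8 / 5 | 0.5 | 2.1 | 0.03 |
| 70 / 8 / 7 | 2.0 | 16 | 0.6 |
| 74 / 8 / 5 | 2.1 | 2.1 | 0.1 |
| 74 / 8 / 7 | 5.7 | 16.0 | 1.5 |
| 74 / 8 / 9 | 12.5 | 36.9 | 5.6 |
| 80 / 11 / 9 | about 43 | about 37 | about 14 |

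The first and last rows are the extremes of the assumed ranges.

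**Would the proposed rows separate the arms?** Five subjects affected, Visit 5, central inputs:

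| Rise | >100 (chance 1.3) | Rise ≥20 (chance 3.8) | Both (chance 0.3) |
|---|---|---|---|
| +20 | 2.7 | 6.2 | 1.3 |
| +25 | 3.6 | 7.1 | 2.2 |
| +30 | 4.5 | 7.9 | 3.2 |
| +40 | 5.7 | 8.6 | 4.7 |

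The contrast is clear in the joint row at +40 and weak in every row at +20 to +25. At +20, the any-visit joint row averages about 2.5 against 1.4, and active exceeds vehicle in only about 61% of trials.

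**The case against.** The strongest case against is that nothing here is an error. The SAP does what Protocol 10.4 asks and adds changes from baseline. Tachycardia that is an untoward occurrence should be reported under Protocol 8.1.4, and it is then counted by arm, severity and visit. What remains is mostly readings that the investigator did not judge untoward, and the protocol reports a low incidence of anticholinergic events so far. Where the new table would separate the arms, the planned maximum already signals (51.5 against 26.8 bpm with five subjects at +40), and the listing identifies them. Where rises are modest, the new table is noisy. Enrolment starts at age 9, and a limit of 100 bpm is not set for children. Dosing is at bedtime and sweat measurement is done between 7:00 and 11:00 am, so clinic pulse is probably taken many hours after application. SAP Section 1 also allows supplementary analyses after lock.

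Most of this stands, and it limits the point to reporting. It does not supply an incidence by arm for unreported readings. Limits chosen after lock could be chosen with the data in view.

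Two stronger readings are tempting. A reader might infer that the plan would conceal a tachycardia signal; the maximum, the listing and the TEAE tables show otherwise. A reader might also infer that readings from subjects who stop early are lost. SAP 9.1 includes them, and only post-baseline unscheduled readings are confined to listings.

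**Conclusion.** The gap is real and small. As written, the plan yields no incidence by arm for a high pulse that was measured but not reported as an adverse event. The gain from closing it is a count by arm, not detection of something otherwise invisible. No planned analysis is invalid, no efficacy conclusion depends on it, and the SAP does not depart from the protocol. This is a cheap improvement for the sponsor to consider.

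The textual finding needs no assumption. Every pulse figure does: mean, both SDs, the number affected and the size and course of the rise are all assumed. Over the ranges tried, chance counts vary widely, and rises of 20 to 25 bpm in a few subjects would show only weakly.

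**What to change.** Add to SAP 9.5.1 and Section 15 one descriptive Safety Population table by arm, giving n (%):

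- **Timing:** each visit, and any on-treatment visit (Visits 5 to 9 and 12, with unscheduled readings counted in the any-visit row). Show Visit 13 separately.
- **All ages:** rise from baseline of at least 20 bpm.
- **Age 17 and over:** also pulse above 100 bpm, and both criteria together.
- **Under 17:** show the high-pulse and joint rows only if the sponsor's medical staff fix age-appropriate limits before unblinding.
- **No hypothesis test,** in line with SAP 9.1.
- **Footnote:** dosing is at bedtime, so clinic readings are probably many hours after application, and a low count does not rule out earlier effects. The limits are for reporting and are not rules for patient care.

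The cost is one table from data already collected, with no change to trial conduct. The downside is that chance exceedances appear in both arms, so the table has meaning only as a comparison with vehicle.

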#### 9.5.2 Physical Examinations

Physical examination results will be collected at Visit 4 only. Physical examination will include assessments of the head, eyes, ears, nose, throat, skin, thyroid, neurological, lungs, cardiovascular, abdomen (liver and spleen), lymph nodes, and extremities. Height and weight will also be measured and recorded. Results of the physical examination will be presented in subject data listings by subject, study visit, and body system.

#### 9.5.3 Other Safety Measures

#### 9.5.3.1 Prior and Concomitant Medications

Medications will be coded using the latest version of the World Health Organization (WHO) drug dictionary. Medications entered on the eCRF will be mapped to Anatomic Therapeutic Chemical (ATC) drug class (level 4) and drug name.

Prior and concomitant medications will be summarized separately and the study phase of each medication will be determined programmatically based on medication start and end dates. Partial or missing start and end dates will be imputed according to Section 9.2.

A prior medication is defined as any medication started prior to the date of the first dose of study drug. A concomitant medication is defined as any medication started on or after the date of the first dose of study drug.

For the summary of both prior medications and concomitant medications, the number and percentage of subjects receiving any medication will be summarized by treatment group,

Version: 2.0 Page 42 of 74

as will the number and percentage receiving any medication by ATC drug class and generic drug name. Subjects reporting use of more than one medication at each level of summarization (any medication received, ATC class, and generic drug name) will be counted only once. ATC class terms will be displayed by descending order of incidence, as will generic drug names within each ATC class. The study phase during which each medication was received (e.g., prior, concomitant,) will be presented on the listing of prior and concomitant medications.

Prior or concomitant therapies and procedures will be listed only.

Version: 2.0 Page 43 of 74

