### 4.3 Exclusion Criteria

Meeting any of the following criteria will exclude a subject from participating in this study:

- 1. In the Investigator's opinion, diagnosis of any skin or subcutaneous tissue conditions of the axilla(e), (i.e., the axillary area should be deemed otherwise "normal", besides the hyperhidrosis diagnosis, and free of blisters, boils or sinus tracts, significant scarring, or open wounds).
- 2. Prior use of any prohibited medication(s) or procedure(s) for the treatment of axillary hyperhidrosis within the specified timeframe:
  - a. Botulinum toxin to the axillary area within 9 months of GSP1 (Visit 2).
  - b. Prior treatment with axillary iontophoresis within 4 weeks of GSP1 (Visit 2)
  - c. Axillary thermolysis, sympathectomy, or any other treatment with a medical device or surgical procedure of the axillary area at any time in the past. Prior axillary laser hair removal is permitted if more than 28 days prior to GSP1 (Visit 2).
  - d. Serotonergic agonist (or drugs that increase serotonin activity including selective serotonin re-uptake inhibitors [SSRIs]), beta-blocker, alpha-adrenergic agonist (clonidine), dopamine partial agonist, or tricyclic antidepressant treatment within 28 days of GSP1 (Visit 2). However, a subject who has been on a stable dose (in the opinion of the Principal Investigator) of any of these medications and has not had a recent change in hyperhidrosis frequency or severity for 3 months prior to the baseline visit may be included. Doses of these agents should not be altered during the course of the study.
  - e. Any topical treatment for hyperhidrosis, requiring a prescription, within 28 days of GSP1 (Visit 2).
  - f. Any over-the-counter topical antiperspirant/deodorant (applied directly to the axilla[e]) within 7 days of GSP1 (Visit 2). Non-antiperspirant deodorant will be provided by the Sponsor.
- 3. Anticholinergic agents used to treat conditions such as, but not limited to, hyperhidrosis, asthma, incontinence, gastrointestinal cramps, and muscular spasms by any route of administration (e.g., intravenous [IV], oral, inhaled, topical, etc.) within 28 days of GSP1 (Visit 2).
- 4. All oral or topical homeopathic or herbal treatment (i.e., alternative therapies such as sage tablets, chamomile, valerian root, and St. John's wort) within 28 days of GSP1 (Visit 2).

- 5. Use of any cholinergic drug (e.g., bethanechol) within 28 days of GSP1 (Visit 2).

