- 6. Use of any anti-anxiety and/or antidepressant drugs, psychostimulants (e.g., amphetamine), or drugs with known anticholinergic side effects is prohibited with the following exceptions:
  - a. A subject who has been on a stable dose of an anti-anxiety and/or antidepressant drug and has not had a recent change in hyperhidrosis frequency or severity for  $\geq 3$  months may be included.
  - b. Psychostimulants may be allowed if the dose has been stable for ≥3 months without change in hyperhidrosis frequency or severity.
  - c. Drugs with known anticholinergic side effects (taken within the last 28 days) including dry mouth or blurred vision may be allowed based on the Investigator's assessment.

NOTE: If anticholinergic side effect(s) are experienced on these medications prior to starting study medication, document the side effect(s) and severities in the source document and the electronic case report form (eCRF). The doses of these agents should not be altered during the course of the study.

- 7. Known cause of hyperhidrosis or known history of a condition that may cause hyperhidrosis (i.e., hyperhidrosis secondary to any known cause such as hyperthyroidism, diabetes mellitus, medications, etc.).
- 8. Subjects with hyperhidrosis symptoms initiated or exacerbated with menopause.
- 9. Subjects with unstable type 1 or type 2 diabetes mellitus or thyroid disease, renal impairment, hepatic impairment, malignancy, glaucoma, intestinal obstructive or motility disease, obstructive uropathy, myasthenia gravis, benign prostatic hyperplasia (BPH), neurological conditions, psychiatric conditions, Sjögren's syndrome, sicca syndrome, or cardiac abnormalities that may alter normal sweat production or may be exacerbated by the use of anticholinergies in the Investigator's opinion.
- 10. Subjects with known hypersensitivity to glycopyrrolate, anticholinergics, or any of the components of the topical formulation.
- 11. Subject is pregnant, lactating, or is planning to become pregnant during the study.
- 12. Participating in a study or used an investigational drug or device within 28 days prior to GSP1 (Visit 2).
- 13. Any major illness within 28 days before the screening examination.

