#### 6 CONCOMITANT MEDICATIONS/TREATMENTS

Information will be recorded on concomitant medications/treatments (e.g., aspirin, Tylenol, birth control pills, intrauterine device [IUD], vitamins) taken during study participation, or which may require a washout for study participation. Every effort should be made to keep dosing with any concomitant medications consistent/constant during the study.

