## 11.2 Compliance with Protocol

At each post-baseline visit, the following activities will occur to ensure compliance with the protocol:

- Subjects will be asked whether they have used the investigational product as instructed.
- Subjects will be reminded to perform ONE FULL pump actuation and use the gel expressed per application to each axilla and asked whether they experienced any problems dispensing the investigational product.
- Subjects will be asked whether they used any other products on their axillae.
- Site staff will review concomitant medication use since the previous visit and determine whether any concomitant medication use qualifies as a protocol deviation
- At each post-baseline visit until EOT, site staff will collect the dispensing container from the subject, then weigh and record the weight of the used container.

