#### 9.2 Adverse Events

Treatment-emergent adverse events (TEAEs) are defined as those adverse events (AEs) with onset during or after the first dose of study drug or existing events that worsened after the first dose during the study. Treatment-emergent AEs will be summarized by treatment group and severity.

Partial or completely missing AE start dates will be imputed as follows:

- 1. If the year and month are known:
  - a. If the year and month are the same as the year and month of the treatment start date, impute to treatment start date.
  - b. Otherwise, use the 1st of the month.
- 2. If only the year is known:
  - a. If the year is the same as the year of treatment start date, impute to treatment start date.
  - b. Otherwise, impute to January 1st of that year.
- 3. If the date is completely missing, impute to treatment start date.

Partial or completely missing AE end dates will be imputed in the same manner, with end of treatment date or end of study date.

AE listings will display the imputed dates.

Verbatim terms on case report forms will be mapped to preferred terms and system organ classes using the latest version of MedDRA.

Version: 2.0 Page 39 of 74

At Visits 5, 6, 7, 8, 9, 12 (EOT), and 13 (Follow-up), treatment-emergent adverse events (TEAEs) in the Safety Population will be summarized by severity in the following tables: all reported TEAEs, all SAEs, all treatment-related SAEs, treatment-related TEAEs, severe TEAEs, TEAEs leading to dose interruption, TEAEs leading to study discontinuation, TEAEs of special interest, and anticholinergic TEAEs. Additionally, local site reaction TEAEs will be summarized in the Safety Population by severity at Visits 5, 6, 7, 8, 9, 12 (EOT), and Visit 13 (Follow-up). Local site reaction TEAEs are defined as AEs coded to the system organ class of general disorders and administration site conditions and, at a minimum, the following preferred terms:

- Application site pruritus
- Application site pain
- Application site irritation
- Application site dermatitis
- Application site rash
- Application site erythema
- Application site discolouration
- Application site dryness
- Application site exfoliation
- Application site reaction
- Application site warmth

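### The SAP separates prior from concomitant medications by start date alone, so drugs begun before first dose and continued on treatment are left out of the concomitant-medication table

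*SAP*

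**What the plan says.** SAP Section 9.5.3.1 gives two definitions. For the first table the SAP says: "A concomitant medication is defined as any medication started on or after the date of the first dose of study drug". A prior medication is one begun before that date. Neither definition mentions the end date or whether the drug is ongoing, so every record falls into exactly one class, and no class exists for drugs started earlier and continued. The two classes are summarized separately for the Safety Population, in Table 14.1.5 (prior) and Table 14.3.6.5 (concomitant).

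Two other sentences in that section point elsewhere. One says that "the study phase of each medication will be determined programmatically based on medication start and end dates". The other says that the medication listing will show "The study phase during which each medication was received". Partial and missing dates follow the adverse-event rules in SAP Section 9.2, where, for a start date: "If the date is completely missing, impute to treatment start date".

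Protocol Section 6 asks sites to record medications "taken during study participation, or which may require a washout for study participation". Protocol Section 11.2 adds, for each post-baseline visit: "Site staff will review concomitant medication use since the previous visit". Protocol Section 4.3 expects some drugs to continue. Exclusion 2d makes an exception for "a subject who has been on a stable dose (in the opinion of the Principal Investigator) of any of these medications", exclusion 6a for "A subject who has been on a stable dose of an anti-anxiety and/or antidepressant drug", and exclusion 6b for psychostimulants at a stable dose.

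**The concern.** A table of concomitant medications is read as a description of what subjects were taking while on study drug. Under the SAP's definitions it describes only what they started after first dose, plus some records moved there by date imputation.

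The drugs lost are relevant ones. Exclusions 2d, 6a and 6b let in subjects on stable treatments, including serotonergic drugs, beta-blockers, tricyclics, anti-anxiety drugs and psychostimulants. Protocol Section 6.2 prohibits adding these drugs or changing their dose during the study. A compliant subject's permitted background drug with a complete start date therefore never enters Table 14.3.6.5. For these classes the table would hold mainly additions that the protocol prohibits and records shifted by imputation. The background drugs would appear in Table 14.1.5, mixed with drugs stopped for washout. If Listing 16.2.4.3 takes its phase label from the same definitions, it carries the same error.

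The section is also inconsistent with itself. A programmer who follows the definitions ignores the end date. One who follows the general sentence about both dates has to invent the rule.

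**Working it through.** The documents state no figure on this point, so there is none to reproduce. The check applies the SAP's rules in sequence to constructed records.

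**Rules.** SAP Section 9.2, start dates:
- Month and year known: treatment start date if the month is the treatment-start month, otherwise the 1st of that month.
- Year only: treatment start date if the year is the treatment-start year, otherwise 1 January of that year.
- Wholly missing: treatment start date.

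SAP Section 9.5.3.1: start before first dose gives prior; start on or after first dose gives concomitant.

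**Assumption.** First dose on 15 June 2021, for illustration only.

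| Recorded start | Actual use | Start after imputation | SAP class | Class by actual use |
|---|---|---|---|---|
| 10 Jan 2019 | ongoing | 10 Jan 2019 | prior | concomitant |
| Jan 2021 | ongoing | 1 Jan 2021 | prior | concomitant |
| 2019 | ongoing | 1 Jan 2019 | prior | concomitant |
| 2021 | ongoing | 15 Jun 2021 | concomitant | concomitant |
| Jun 2021 | ongoing | 15 Jun 2021 | concomitant | concomitant |
| missing | ongoing | 15 Jun 2021 | concomitant | concomitant |
| 10 Jan 2019 | stopped 1 Apr 2021 | 10 Jan 2019 | prior | prior |
| 2019 | stopped 1 Apr 2021 | 1 Jan 2019 | prior | prior |
| 2021 | stopped 1 Apr 2021 | 15 Jun 2021 | concomitant | prior |
| missing | stopped 1 Apr 2021 | 15 Jun 2021 | concomitant | prior |

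**Result.** Of 6 drugs taken throughout treatment, 3 are classed prior, and so are missing from Table 14.3.6.5. Of 4 drugs stopped before dosing, 2 are classed concomitant. Together 3 + 2 = 5 of 10 records disagree with actual use.

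**Sensitivity to the assumed date.** With first dose on 15 March 2021, continuing drugs with starts of 10 Jan 2020, 2020 (imputed 1 Jan 2020) and Feb 2021 (imputed 1 Feb 2021) are prior. Those with starts of Mar 2021, 2021 and missing are all imputed to 15 March 2021 and are concomitant. The split is again 3 and 3.

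**Two mechanisms.** The first three rows fail because the definition looks only at the start date. The last two fail because imputation puts the start after a known end date and nothing checks it. Using the end date in the definition corrects both: the 6 ongoing records become concomitant and the 4 records that ended on 1 April 2021 become prior, leaving 0 of 10 misclassified.

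**The case against.** The strongest objection has five parts.

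- **The SAP may intend an end-date rule.** It mentions end dates, has them imputed, and gives the listing labels only as examples. The table and listing specifications are in a separate document that is not available here. This has some force for the listing: its label is wrong only if it follows the definitions. For the tables, the definitions are the only rule stated, and they ignore the end date.
- **The protocol text is not an analysis definition.** Section 6 tells sites what to record and expressly includes washout drugs; Section 11.2 is a compliance check. That is right, and neither sets a boundary at first dose. The case therefore rests mainly on the conflict within SAP Section 9.5.3.1.
- **The count of 5 in 10 has no empirical meaning.** The records were constructed, and another mix would give another fraction. This stands. The table shows which kinds of record are misclassified, not how many there will be.
- **The remedy moves the dependence to end dates.** SAP Section 9.2 imputes missing end dates to the end of treatment or study. A washed-out drug whose end date is missing, or known only as the treatment year, would then count as concomitant. This is true, but in those cases it follows the plan's own convention of assuming continued use, and it does not undo the correction for records with usable end dates.
- **Little depends on it.** Prohibited medication is handled as a major protocol violation in SAP Section 5.2, and interfering medication as a per-protocol criterion in SAP Section 4. Neither is tied to this classification. All records are listed, and earlier-started drugs still appear by arm in Table 14.1.5. This stands and sets the limit on importance.

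**Conclusion.** The concern holds. As written, any drug with a recorded or imputed start before first dose is prior only, however long it continues, and Table 14.3.6.5 will not describe medication use during treatment. This is a stated rule that gives the wrong table, not a detail left open.

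The conclusion rests on reading the two definitions as the operative rule. How many records are affected cannot be estimated, because the documents give no figures on medication use or date completeness. The consequence is confined to descriptive Safety Population displays: the two tables and, on the same reading, the phase label in the listing. No efficacy test, alpha level, sample size or analysis population changes. The definitions should be corrected, but they do not threaten the trial's main conclusions.

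**What to change.** In SAP Section 9.5.3.1, define a concomitant medication as any medication taken on or after the date of first dose, including one started earlier that is ongoing or whose end date falls on or after first dose. Define a prior medication as one stopped before first dose. Each record then has one phase, and the definitions agree with the section's own reference to both dates.

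An acceptable alternative keeps prior as started before first dose and lets a continuing drug count in both tables. In that case the SAP must also say that an imputed start date may not fall after a known end date. Otherwise a washed-out drug with a missing start and an end date of 1 April 2021 would have its start imputed to 15 June 2021 in the example above, and would meet neither definition.

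Under either option, state that a missing end date, or one known only as the treatment year, leads to the drug being counted as concomitant under the Section 9.2 convention, so that readers know which way the remaining uncertainty falls.

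The cost is one or two SAP sentences for the definitions, that clarifying line, and one programming condition. No new data are needed, since the section already relies on both start and end dates.
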